## 6. A Priori Statistical Methods

### 6.1. General Considerations

Unless otherwise specified, efficacy analyses will be conducted on the Intent-to-Treat (ITT) Population. Patients will be analyzed according to the treatment to which they were assigned. All tests of treatment effects will be conducted at a 2-sided alpha level of 0.05, unless otherwise stated.

**Table KHAA.6.1. General Methods for Statistical Analysis**

Data Type	Purpose	Analysis
Categorical/discrete data	Summary and descriptive analysis	Number of patients with available data (n), either observed or imputed, at the relevant time point, and will be presented as frequency counts and percentages. Percentages will be calculated using the total number of patients in the analysis population included as the denominator. Percentages will generally be presented to 1 decimal place but will not be presented for zero counts.
	Treatment comparison	Logistic regression analysis
Continuous data	Summary and descriptive analysis	Number of observations, mean, standard deviation (SD), standard error of the mean (SEM), median, 1st quartile, 3rd quartile, minimum, and maximum. The minimum and maximum will be reported to the same number of decimal places as the raw data recorded in the database. The mean, first quartile, median, and third quartile will be reported to 1 more decimal place than the raw data recorded in the database. The SD and SEM may be reported to 2 more decimal places than the raw data recorded in the database. Any exceptions will be noted in the programming specifications. P-values for primary and key secondary analyses will be reported to as many decimal places as needed ( $\geq 5$ ).
	Treatment comparison	Analysis of variance (ANOVA), mixed model repeated measures (MMRM), Wilcoxon rank-sum test
Ordinal data	Treatment comparison	Proportional Odds model, Wilcoxon rank-sum test
Time to event data	Treatment comparison	Log-rank test, Kaplan-Meier curves, Cox proportional hazards. As needed: Fine-Gray model, Max-combo test

Note: the detail of the analysis method defined in Section 6.2.

Change from baseline will be calculated as the visit value of interest minus the baseline value. If the baseline value is missing for a particular variable, then it will not be imputed and the change from baseline and percent change (or percent improvement) from baseline will not be calculated.

For all models, patients will be excluded who do not have the necessary covariates to run the model.

For the primary and key secondary analyses that rely on OS values, the patient's worst ordinal score for the day will be used.

The Per Protocol Set (PPS) will be used if needed for post hoc analyses.

Throughout this document, "Day x" refers to Study Day x.

Additional supportive analyses will be performed as needed.

### 6.1.1. Analysis Populations

The following populations are defined for this study:

Population	Description
Entered	All participants who sign the informed consent form
Intent-to-Treat (ITT)	All participants randomly assigned to study intervention. Participants will be analyzed according to the intervention to which they were assigned.
Per Protocol Set (PPS)	The PPS will include those participants in the ITT population who do not have any identified important protocol violations considered to impact efficacy analyses. Qualifications for, and identification of, significant or important protocol violations will be determined while the study remains blinded, prior to database lock.
Safety	All participants randomly assigned to study intervention and who receive at least 1 dose of study intervention and who did not discontinue from the study for the reason 'Lost to Follow-up' at the first postbaseline visit. Participants will be analyzed according to the intervention they actually received.
Follow-up	All randomized participants who received at least 1 dose of investigational product and have entered the post-treatment follow-up period. Participants will be analyzed according to the intervention to which they received.

A listing of patients who were randomized but did not receive study drug will be prepared. This listing will include baseline information and their last known status.

A sensitivity analysis for the primary efficacy analysis will exclude patients who die within 24 hours of randomization and have Do Not Resuscitate (DNR) or Do Not Intubate (DNI) in ITT analysis populations will be conducted.

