Site Visit		X	X	X	X	X					Site visit is preferred after discharge, but telephone visit is acceptable after discharge and should include collection of concomitant medications, adverse events, COVID-19 clinical symptoms, and Clinical Status Assessment. Failure to conduct activities that cannot be reasonably performed over the telephone will not be considered a protocol deviation.
Telephone Visit							X	X			
Prespecified medical history: comorbidities	X										Includes comorbidities such as, but not limited to, diabetes, hypertension, cardiovascular disease, underlying pulmonary disease.
Prespecified medical history: COVID-19	Х										Includes COVID-19 diagnosis date and onset of COVID-19 symptoms.
Prior treatments of special interest within last 2 weeks	X										Includes NSAIDs, antivirals, antibiotics, antimalarials, corticosteroids, herpes zoster vaccine, immunosuppressive medications.
Substance use (tobacco use)	Х										
Concomitant medications	Х	Х	Х	Х	Х	Х	Х	Х	Х		Assess daily. Includes medications of interest: background therapy, supportive care, sedating/paralytic drugs, and VTE prophylaxis.
Adverse events (AEs)	X	Х	Х	Х	Х	Х	Х	Х	Х		Assess daily. AE collection begins when ICF is signed. For infections and VTEs, additional data are collected (Section 8.3.6).
COVID-19 clinical symptoms	Х	Х	Х	Х	Х	Х	Х	Х	Х		Assess daily while hospitalized and on day of visits after discharge.

Study day	1	4	7	10	14	28	Follow-up (28 Days after Last Dose)	Follow-up Day 60	ETV	Unsched uled	Comments
Interval tolerance (days)	≤3	_	_	_	_	_	±4	+7	_	_	If patient is discharged from hospital, the study visit may include a visit interval tolerance (window) of $\pm 2$ at Study Day 4, Day 7, Day 10, Day 14, and Day 28.
Site Visit		X	X	X	X	X					Site visit is preferred after discharge, but telephone visit is acceptable after discharge and should include collection of concomitant medications, adverse events, COVID-19 clinical symptoms, and Clinical Status Assessment. Failure to conduct activities that cannot be reasonably performed over the telephone will not be considered a protocol deviation.
Telephone Visit							X	X			
Clinical Assessments											
Height	Х										May be as measured or reported.
Weight	Х										
Vital signs	X	X	Х	X	X	X			X		Assess and document daily while hospitalized. Includes: respiratory rate and oxygen saturation, blood pressure, body temperature, heart (pulse) rate. See Section 8.2.1.

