# 6.4. Study Intervention Compliance

Participants will receive study intervention directly from the investigator and/or appropriate designee at the study site. The date and time of each dose administered will be recorded in the source documents and recorded in the case report form (eCRF). Deviations from the prescribed dosage regimen should be recorded in the eCRF.

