# 8.3.1. Time Period and Frequency for Collecting Adverse Event and Serious Adverse Event Information

All adverse events will be collected from the time of the participant's signing of the ICF until the participant's last post-treatment follow-up visit. Adverse events will be recorded on the Adverse Event eCRF.

Likewise, all SAEs will be collected from the signing of the ICF until the last post-treatment follow-up visit.

Although all adverse events after signing the ICF are recorded by the site in the CRF/electronic data entry tool, SAE reporting to the sponsor begins after the participant has signed the ICF and has received study drug. However, if an SAE occurs after signing the ICF but prior to receiving study drug, the SAE needs to be reported ONLY if the SAE is considered reasonably possibly related to study procedures.

SAEs will be recorded and reported to the sponsor or the sponsor's designee immediately, and under no circumstance should this exceed 24 hours, as indicated in Appendix 10.3. The investigator will submit any updated SAE data to the sponsor within 24 hours of it being available. Serious adverse events, including death, caused by COVID-19 disease progression should not be reported on the SAE form unless the investigator deems them to be possibly related to study treatment (Appendix 10.3).

Investigators are not obligated to actively seek adverse events or SAEs after the conclusion of study participation, that is, once the participants have discontinued and/or completed the study (the Participant Study Disposition eCRF has been completed). However, if the investigator learns of any SAE, including a death, at any time after a participant has ended his or her study participation, and the investigator considers the event to be reasonably related to the study intervention or study participation, the investigator must promptly notify the sponsor.

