## 9.4.4. Safety Analyses

Safety analyses will include adverse events (AEs), serious adverse events (SAEs), adverse events of special interest (AESIs), vital signs, and laboratory analytes, using the Safety Population. Continuous safety measures will be summarized as mean change by visit and analyzed using ANCOVA with treatment and baseline value in the model. For binary safety measures, Fisher's exact test will be used to perform comparisons between the baricitinib 4-mg QD + background

therapy group and the placebo + background therapy group. Further analyses may be performed, and details of the analyses will be included in the SAP.

Exposure to study intervention will be calculated for each participant and summarized by treatment group.

Adverse events will be coded according to the Medical Dictionary for Regulatory Activities (MedDRA) and summarized by system organ class, preferred term, and severity. A treatmentemergent adverse event (TEAE) is defined as an event that either first occurred or worsened in severity after the first dose of study treatment and on or prior to the last visit date during the analysis period. Safety analyses will be conducted separately for the double-blind treatment period and the post-treatment follow-up period. For events that are gender-specific, the denominator and computation of the percentage will include only participants from the given gender.

Adverse events of special interest will be identified by a standardized MedDRA query (SMQ) or a Lilly-defined MedDRA preferred term list. The number and percentage of participants who experienced TEAEs, TEAEs by maximum severity, deaths, SAEs, permanent discontinuations from the treatment due to an adverse event, incidence of abnormal values, and AESIs will be summarized. TEAEs (all, by maximum severity), SAEs including deaths, and adverse events that lead to treatment discontinuation will be summarized and analyzed by MedDRA system organ class and preferred term.

All clinical laboratory results will be descriptively summarized by treatment group. Individual results that are outside of normal reference ranges will be flagged in data listings. Shift tables will be presented for selected laboratory measures.

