**Table KHAA.6.5. Description of Primary, Key Secondary, and Associated Supportive Analyses**

Measure	Variable	Population	Analysis Method	Time Point	Analysis Type
NIAID-OS	Proportion of patients who died or progressed to non-invasive ventilation or high-flow oxygen (OS $\geq$ 6)	ITT: Population 1 - all randomized patients	Logistic regression using MI	By Day 28	Primary analysis
		ITT: Population 2 – patients who, at baseline, require oxygen supplementation and are not receiving dexamethasone or other systemic corticosteroids for the primary study condition.	Logistic regression using MI	By Day 28	Primary analysis
		ITT	Logistic regression using LOCF	By Day 28	Supportive analysis
		ITT: Population 2	Logistic regression using LOCF	By Day 28	Supportive analysis
		Safety Population	Logistic regression using MI	By Day 28	Supportive Analysis
		ITT Population, excluding patients who die within 24 hours of baseline and have Do Not Resuscitate (DNR) or Do Not Intubate (DNI) orders	Logistic regression using MI	By Day 28	Sensitivity Analysis
		Ventilator free days (VFD)	ITT	ANOVA using MI	By Day 28
	Wilcoxon rank-sum test using LOCF			By Day 28	Supportive analysis
	Proportion of patients with 1-point improvement	ITT	Logistic regression using MI	Day 4, 7, 10, 14	Key secondary analysis
			Logistic regression using LOCF	Day 4, 7, 10, 14	Supportive analysis

Measure	Variable	Population	Analysis Method	Time Point	Analysis Type
	Time to recovery	ITT	Log-rank test using IETI	By Day 28	Key secondary analysis
			Cox proportional hazards model using IETI	By Day 28	Supportive analysis
			Max-combo test using IETI (if needed)	By Day 28	Supportive analysis
NIAID-OS	Overall improvement	ITT	Proportional odds model using MI	Day 4, 7, 10, 14	Key secondary analysis
			Proportional odds model using LOCF	Day 4, 7, 10, 14	Supportive analysis
	Duration of hospitalization	ITT	ANOVA using MI	By Day 28	Key secondary analysis
			Wilcoxon rank-sum test LOCF	By Day 28	Supportive analysis
	All-cause mortality	ITT	Log-rank test	By Day 28	Key secondary analysis
			Cox proportional hazards model	By Day 28	Supportive analysis
Safety					
			Log-rank test	By Day 28	Supportive analysis
			Cox proportional hazards model	By Day 28	Supportive analysis
Oxygen Saturation	Proportion of patients with change in oxygen saturation from <94% at baseline to $\geq$ 94% at the observed time point	ITT	Logistic regression using LOCF	Day 4, 7, 10, 14	Key secondary analysis

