#### **6.13. Safety Analyses**

The planned safety analyses are consistent with compound level safety standards, which are based on various sources, including company standards, internal and external subject matter experts, and cross-industry initiatives (for example, white papers produced by a Pharmaceutical Users Software Exchange [PhUSE] Computational Science Working Group [a collaboration with Food and Drug Administration (FDA) and PhUSE], published in the PhUSE Deliverables Catalog [PhUSE [WWW]]. Descriptions of the safety analyses are provided in this SAP; however, some details are in compound level safety standards.

A treatment-emergent adverse event (TEAE) during the analysis period is defined as an event that either first occurred or worsened in severity after the first dose of study treatment and on or prior to the end of the postbaseline period (defined as Day 28 for the primary outcome datalock).

A follow-up-emergent adverse event (FEAE) is defined as an event that either first occurred or worsened in severity after the treatment period and on or prior to the last visit date during the post-treatment follow-up period (up to the Day 60 visit) of the study.

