**Table KHAA.6.9. Summary Tables Related to Adverse Events**

Analysis	Population or Analysis Set
An overview table, with the number and percentage of subjects who experienced a TEAE, serious adverse event, death, discontinued from study treatment due to an adverse event	Safety population
An overview table, with the number and percentage of subjects who experienced an event, serious adverse event, death, discontinued from study due to an adverse event	Follow-up analysis set
The number and percentage of subjects with TEAEs using MedDRA Preferred Term nested within System Organ Class	
The number and percentage of subjects with FEAEs using MedDRA Preferred Term nested within System Organ Class	Follow-up analysis set
The number and percentage of subjects with TEAEs using MedDRA Preferred Term	Safety population
The number and percentage of subjects with TEAEs by maximum severity using MedDRA Preferred Term	Safety population
The number and percentage of subjects with TEAEs using MedDRA Preferred Term for the common TEAEs (occurred in $\geq 2\%$ before rounding of treated subjects)	Safety population
The number and percentage of subjects who experienced a serious adverse event (including deaths and SAEs temporally associated or preceding deaths) using MedDRA Preferred Term nested within System Organ Class	Safety population
The number and percentage of subjects who experienced a serious adverse event (including deaths and SAEs temporally associated or preceding deaths) using MedDRA Preferred Term nested within System Organ Class	Follow-up analysis set
Listing of All SAEs	Safety population
The number and percentage of subjects who permanently discontinued from study treatment due to an adverse event (including adverse events that led to death) using MedDRA Preferred Term nested within System Organ Class	Safety population
Listing of AEs which led to permanent discontinuation from the study treatment and from the study	Safety population

Abbreviations: AEs = adverse events; ITT = Intent-to-Treat; MedDRA = Medical Dictionary for Regulatory Activities; SAE = serious adverse event; TEAE = treatment-emergent adverse event.

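### The Safety Population leaves out dosed participants lost to follow-up at the first postbaseline visit, so any exposure and post-dose adverse events recorded for them would be missing from the safety outputs that use it

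*SAP*

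**What the plan says.** SAP 6.1.1 and Protocol 9.3 set three conditions for the Safety Population: randomized, at least one dose received, and a participant "who did not discontinue from the study for the reason 'Lost to Follow-up' at the first postbaseline visit". Participants are analysed by the treatment they received. The clause is the same in both documents, so it is the operative rule and not a slip in one of them.

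Other sections describe what is recorded before any such loss:

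- Adverse events, Protocol 1.3: "Assess daily. AE collection begins when ICF is signed".
- Collection window, Protocol 8.3.1: "All adverse events will be collected from the time of the participant's signing of the ICF until the participant's last post-treatment follow-up visit".
- Dosing, Protocol 6.4: "The date and time of each dose administered will be recorded in the source documents".
- Treatment-emergent adverse event, SAP 6.13: "an event that either first occurred or worsened in severity after the first dose of study treatment".

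Protocol 9.4.4 places adverse events, vital signs and laboratory data on this set ("laboratory analytes, using the Safety Population"). In SAP Table KHAA.6.9 the treatment-period outputs that name a population name this one, including the row "Listing of All SAEs". SAP Table KHAA.6.5 also uses the "Safety Population" for a supportive analysis of the primary endpoint and for supportive mortality analyses.

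**The concern.** A clause of this kind does no harm where someone lost before the first visit has contributed no safety data. This trial is different. Participants are inpatients, site staff give the drug, and events are recorded every day. A participant who leaves hospital early and cannot be reached afterwards may already have documented doses and documented adverse events.

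At stake is whether the safety denominator is everyone who was dosed. For common events, a few missing participants hardly matter. For rare events of interest, such as venous thromboembolism (which Protocol 2.3 classes as an important potential risk), one case more or less can be visible in a by-arm count. The exclusion also depends on something that happens after randomization, and a safety set is better defined without such a condition.

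**Working it through.** The documents give no count or rate of early loss, so there is no stated figure to reproduce. The check compares the rules and then gives a size under stated assumptions.

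**1. Who is removed.** Only participants who were dosed and whose recorded reason for discontinuing is loss to follow-up, at the first postbaseline visit. Those who die, withdraw consent or stop because of an adverse event stay in.

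**2. What they could have on record.** Each dose with date and time (Protocol 6.4), daily adverse events from consent (Protocol 1.3 and 8.3.1), and daily vital signs while in hospital (Protocol 1.3).

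**3. Whether those events would otherwise count.** They would. The SAP 6.13 definition runs from the first dose, and in SAP Table KHAA.6.8 the postbaseline period also begins after the first dose. Neither requires a postbaseline visit. The population rule is therefore narrower than the SAP's own event definition.

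**4. Whether another planned output restores them.**

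| Output or population | Covers dosed participants lost at the first visit? |
|---|---|
| Follow-up population (SAP 6.1.1) | No. It requires entry into post-treatment follow-up, which SAP Table KHAA.6.2 ties to having had a follow-up visit. |
| Extra listing in SAP 6.1.1 | No. It covers randomized participants who were never dosed. |
| Disposition listing (SAP 6.7) | Yes, but it carries no adverse events. |
| By-participant event listing (Protocol 9.4.4) | Unclear. It stands under the post-treatment follow-up heading, where analyses use the follow-up population. |
| Exposure summary (SAP 6.13.1), registry event summary (SAP 6.19) | Unclear. No population is named there. |
| Mortality by Day 28 (SAP Tables KHAA.6.4 and 6.5) | Yes for known deaths; the key secondary analysis is on the intent-to-treat population. |

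None of the defined populations is simply all dosed participants, and no adverse event output clearly brings these participants back.

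**5. Size.** Planned enrolment is about 1400, randomized 1:1, so about 700 per arm. If a share s of participants were removed, the number is 1400 × s. For s = 0.1%, 1400 × 0.001 = 1.4. For s = 1%, 1400 × 0.01 = 14. Both shares are assumptions, and zero is also possible.

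As a worst case, suppose k participants are removed from one arm and every one of them had the event. With e events among 700, the rate moves from e/700 to (e − k)/(700 − k). The event rates are assumed:

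| Events e (rate) | k = 1 | k = 4 | k = 7 |
|---|---|---|---|
| 7 (1.00%) | 6/699 = 0.86% | 3/696 = 0.43% | 0/693 = 0.00% |
| 35 (5.00%) | 34/699 = 4.86% | 31/696 = 4.45% | 28/693 = 4.04% |
| 105 (15.00%) | 104/699 = 14.88% | 101/696 = 14.51% | 98/693 = 14.14% |

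The columns for k = 4 and k = 7 are bounds rather than expectations: they need every removed participant to be in the same arm and to have had the event.

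**The case against.** The strongest reply is that the clause may remove nobody. Protocol 7.3 reserves loss to follow-up for participants who repeatedly miss scheduled visits and cannot be contacted, which one missed visit hardly satisfies. Exclusion criterion 16 keeps out patients whose discharge, or transfer away from the study site, is anticipated within 72 hours. After discharge, visits have a window of 2 days either way and can be done by telephone. Protocol 7.2 expects withdrawal from the study to be uncommon. All of this stands, and it is why the point is small. It does not justify the clause: a rule that removes nobody is not needed, and a rule that removes somebody removes recorded data.

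The second reply is that neither document defines the first postbaseline visit. Day 4 is the first scheduled column after Day 1, but status and adverse events are recorded daily, with a clinical status entry on Day 2. On the narrow reading very little post-dose data would be lost. This also stands. A reader might take it as settled that up to three days of dosing are lost per participant, but the documents do not fix that figure.

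The third reply is that serious events remain under oversight. Protocol 8.3.1 requires serious adverse events to reach the sponsor within 24 hours, apart from COVID-19 progression events not deemed possibly related to treatment. Protocol 8.3.6 sends all suspected venous thromboembolic events to a blinded committee. Neither step is limited to the Safety Population. This stands, so the gap lies in the planned tables and listing, not in safety reporting. Some safety analysis details are also in compound-level standards that are outside these documents, so it cannot be said that the data drop out of every output.

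**Conclusion.** The point holds in a limited and conditional form. If any dosed participant is classed as lost to follow-up at the first postbaseline visit, that participant's recorded exposure and post-dose events are left out of the treatment-period adverse event tables and the serious adverse event listing wherever these name the Safety Population. The number affected is not given; on an assumed 0 to 1% it is 0 to 14 of 1400, and it may well be zero. The effect on common event rates would be negligible. For a rare event, a single case could change a by-arm count.

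Two stronger readings are tempting. A reader might infer that early loss depends on treatment and so biases the comparison between arms. Nothing in the documents shows this in a double-blind trial, and it remains speculation. A reader might also infer that the efficacy conclusions are affected. They are not: primary and key secondary inference is on the intent-to-treat population, known deaths by Day 28 stay in that mortality analysis, and the rows of SAP Table KHAA.6.5 that use the Safety Population are supportive only.

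**What to change.** Delete the lost-to-follow-up clause in SAP 6.1.1 and in Protocol 9.3. The Safety Population is then all randomized participants who receive at least one dose, analysed by the treatment received. If the clause has to stay, define the first postbaseline visit, and list by arm the exposure and adverse events of each dosed participant it removes.

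The cost is one clause in each document. The drawbacks are a departure from what appears to be a standard definition, and a few participants with short follow-up in the denominator. The supportive analyses on this set already allow for incomplete follow-up, by multiple imputation for the primary endpoint and by censoring for mortality, so they need no other change.
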